3. Participant will be asked to provide pain level on 11-point (0-10) NRS immediately before study drug ingestion as the baseline pain score. Baseline symptoms (sedation and dizziness) will also be recorded.
4. Women will ingest the assigned gabapentin 600 mg or placebo
 - a. Stratified block randomization will occur to achieve even distribution of women based on vaginal parity (no prior vaginal delivery versus one or more prior vaginal deliveries). This strategy will ensure similar numbers of women with vaginal parity between gabapentin and placebo groups as this may be an important factor influencing pain with dilators in general.
 - b. A UC Davis Investigational Drug Services (IDS) pharmacist will use computer-generated randomization to place active or placebo treatment in two groups of sequentially numbered vials (to account for block randomization based on parity)
5. The physician will proceed with dilator insertion via our existing standardized method (including standard cervical anesthesia with 1% xylocaine 20 mL, standard number of dilators based on gestational age). Number of dilators and any pharmacologic means of cervical preparation are already reported in a standardized template and will be available for chart review.
6. Post-dilator pain will be assessed via NRS at five minutes after dilator insertion. Additional symptoms (sedation and dizziness) will be recorded.
7. Women will be discharged home with:
 - a. One additional study medication (Gabapentin 600 mg or placebo) to take at home 8 hours after the initial dose. This medication will be labeled by the IDS and completed by administering physician.
 - b. Standard prescriptions for acetaminophen 300 mg/codeine 30 mg and ibuprofen 800 mg to take as needed.
 - c. A reminder form that includes 24-hour research contact information, the times when they can expect text messages, a reminder to take the home dose of their assigned study medication at 8 hours after dilator insertion (exact time will be written out) and a reminder to bring the empty study medication bottle with them when they present for their procedure the next day.
 - d. Recommendation that they have a ride to and from abortion procedure the subsequent day.
8. Participants will be sent a baseline text message from the study phone prior to leaving the clinic. Participants will be encouraged to enable privacy features on their personal phone. Examples of security features will be reviewed and included in the consent.

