9. Participants will be contacted via text message at 2, 4, and 8 hours after dilator insertion.
 - a. Text messages will originate from a password protected study cell phone. Android application "SMS scheduler" will be used to send standardized text messages to the participant at pre-programed time intervals from time of dilator insertion.
 - b. Text message content:
 - i. Current NRS pain score
 - ii. Inventory of analgesic use since last contact
 - iii. Presence of symptoms (sedation and dizziness)

PROTOCOL TITLE: Gabapentin for pain control after osmotic dilator insertion and prior to D&E procedure: a randomized controlled trial

- iv. Reminder to take the assigned study medication (at 8 hours only)
10. Upon admission to the pre-operative ward prior to D&E, we will document the time and assess the current NRS pain score, additional analgesic use since 8 hour text message contact, and presence of symptoms (sedation and dizziness)

Blinding

Participants and providers will be blinded to study drug allocation as all study drug will be prepared by the pharmacist and placed into numbered drug bottles.

Privacy protection

Participant privacy is another ethical concern in this study. Participants may have people with access to their cell phones who do not know about the pregnancy or abortion. Compromising a woman's privacy about this matter could put her at risk depending on her life situation. To prevent this, I plan to use generic language that does not identify the context of the woman's care. Women will be counseled regarding their ability to rescind their participation at any point. Below is the verbatim content of each text message that will be sent to participants. These text messages will be sent in order, with a programmed one-minute interval between each question:

1. "What is your current pain level on a scale of 0-10? (Zero is no pain and ten is the worst pain imaginable)"
2. "How many pills of ibuprofen have you taken since the last text?"
3. "How many pills of acetaminophen with codeine have you taken since the last text?"
4. "Do you feel more dizzy than usual?"
5. "Do you feel more tired than usual?"

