Interest in gabapentin for perioperative pain management is increasing in part due to its favorable safety profile. There are few contraindications to gabapentin use. It is excreted by the kidneys unchanged from its ingested form. [26] The absence of hepatic metabolism enables use in patients with hepatic disease or on medications that influence hepatic enzymes. [26] Renal insufficiency can increase the clearance time of gabapentin so dosage adjustment or avoidance of gabapentin is needed depending on the severity of renal disease. [26] Gabapentin is well tolerated in the pediatric population as well. [26] Most common side effects include dizziness and somnolence with less common reporting coordination or balance issues, peripheral edema, or gastrointestinal symptoms. [26] These reports are among chronic users of gabapentin. Studies investigating perioperative use focus more on immediate side effects experienced by gabapentin naïve patients such as dizziness and somnolence. [26]

Study drugs will be obtained from the UC Davis Investigational Drug Services (IDS). The IDS is a division of UC Davis Pharmacy Services that can procure gabapentin and over-encapsulate it to match an identical placebo. The IDS controls participant randomization, maintains randomization log, and provides additional support for study drug administration along with accountability and adherence with state drug dispensing regulations. The IDS has already reviewed this research study and has formulated a plan for study execution with investigators. [name] (Senior IDS Pharmacist) has shadowed the Principal Investigator in the preoperative clinic to formulate a concrete plan for IDS drug preparation and medication accountability.

Participant Compensation:

Participants will be compensated \$30 for initial study drug ingestion and completing baseline data collection. They will be provided based on fully answering all five text messages at each scheduled encounter. Compensation will include an additional \$10 for completion of 2 hour and 4 hour text messages, and \$20 for the 8 hour contact. Participants will receive a final \$30 for completion of the assessment when presenting for D&E. Compensation will occur via gift cards provided to participants when presenting for their procedure the subsequent day. Maximum compensation per participant will be \$100, with partial compensation possible based on participation level. Participants will be provided with the compensation levels.

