PROTOCOL TITLE: Gabapentin for pain control after osmotic dilator insertion and prior to D&E procedure: a randomized controlled trial

8) Data and/or Specimen Management and Confidentiality

Sample size calculation

For the purpose of calculating sample size, there is no existing data that truly mirrors the objective of this study (context of pain, use of NRS, and use of change in pain score from baseline). The closest approximation is the mean immediate post-dilator insertion pain score of 5.2 (SD 1.2) via NRS from Borgatta, et al (2012). However, when using this data point and a commonly cited clinically significant decrease in NRS pain score of 2 points, computation with SAS 9.1 (factoring in power at 80% ($\alpha=0.05$), normal distribution) yielded a small sample size of only 12 women per group. [27-33] Based on the block randomization there are four groups for a total of 48 women. To account for up to 20% of subjects not responding to text messaging for the primary outcome the sample size estimate will increase to 58 total women. To ensure we gather sufficient data to truly outline pain experience during the dilator-procedure interval, we will more than double the sample size to recruit 121 women. We will stratify these 121 women by presence or absence of prior vaginal parity. Ensuring similar distribution of vaginal parity between the gabapentin and placebo groups is important as vaginal parity may affect pain with osmotic dilators.

Statistical Analysis

We will use non-parametric testing to assess the primary outcome variable because we do not expect normal distribution of the data. Chi square analysis and fisher exact tests will be used to compare demographics and dichotomous variables as appropriate. I plan to describe the pain course for the total study cohort using means and medians as appropriate.

Data Management

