The FDA label for gabapentin lists adverse events reported by studies investigating the drug for management of either epilepsy or postherpetic neuralgia. Both FDA approved indications for gabapentin use a wide range of drug dosing and a significantly longer duration compared to this study. Studies investigating gabapentin for peri-procedure analgesia are powered to detect their primary outcome of pain reduction. Those studies reporting side effects ask about sedation and dizziness most commonly. [34] Gynecologic studies, typically in the context of abdominal hysterectomy, report no statistically significant increase in sedation or dizziness compared to placebo. [13-14] Both studies started with initial doses of gabapentin 1200 mg, which is twice the dosing of this study.[13-14] Dierking et al continued gabapentin dosing for a total of 3000 mg over 24 hours (year). While

PROTOCOL TITLE: Gabapentin for pain control after osmotic dilator insertion and prior to D&E procedure: a randomized controlled trial

participants may be able to understand the FDA risk stratification, delineating frequent, infrequent, and rare adverse events, the risks in the label do not accurately simulate the clinical context of this study.

To minimize risks, the dose of Gabapentin used in this study is comparable to that of prior peri-procedure studies and the same as an ongoing randomized controlled trial through the family planning division at Emory University that is investigating Gabapentin 600 mg versus placebo for pain control during first trimester aspiration abortion. [25] Out of caution, participants will be required to have a ride home from the clinic as criteria for study eligibility so they aren't driving after study medication dosing. Frequency of reported side effects will be closely monitored, as well as any AE or SAEs, per Section 11.

2. *Privacy risk:*

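### Home sedation and dizziness are recorded only when a woman answers a text, and the plan has no provision for symptom replies that are missing

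*Combined protocol and SAP*

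**What the plan says.** The plan treats sedation and dizziness as the symptoms to watch. Section 7 (Study drug) states "Most common side effects include dizziness and somnolence", and Section 12 promises that "Frequency of reported side effects will be closely monitored".

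Section 7 sets out when they are measured:
- In clinic before study drug: "Baseline symptoms (sedation and dizziness) will also be recorded".
- In clinic five minutes after insertion: "Additional symptoms (sedation and dizziness) will be recorded".
- At home: "Participants will be contacted via text message at 2, 4, and 8 hours after dilator insertion". Each contact is five questions sent one minute apart. Dizziness is the fourth. The fifth, about four minutes after the first, is "Do you feel more tired than usual".
- On pre-operative admission (step 10): pain, analgesic use since the 8-hour contact, and presence of the two symptoms. The period is attached to analgesic use. None is stated for symptoms.

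Section 8 mentions non-response once, in the sample size calculation: "To account for up to 20% of subjects not responding to text messaging for the primary outcome". The analysis text for yes/no variables is one sentence: "Chi square analysis and fisher exact tests will be used to compare demographics and dichotomous variables as appropriate". It does not name the symptoms, define an analysis set, or say what happens when a reply is missing.

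**The concern.** Sedation can itself be the reason that a sedation answer is missing. A woman who is asleep, or too drowsy to reach the fifth question, leaves a blank. As nothing else is specified, the natural reading of Section 8 is that the tests will use those who replied. Non-response is not compared between arms, and nobody asks why a round was missed. Because the admission check states no look-back, an episode of drowsiness that silenced a woman at home and had passed by morning need not be recorded anywhere.

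What is at stake is the credibility of the tolerability statement for the hours at home. The trial could report sedation rates that are too low in both arms, with nothing in the report to show how much depends on the women who did not answer.

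**Working it through.** **1. The plan's own non-response figure.** Section 8 raises 48 women by 20%: 48 × 1.2 = 57.6, rounded up to 58, as printed. Recruitment is then set at 121. With 20% silent, about 121 × 0.8 = 97 women would have a reply at a given time, or about 48 of 60 per arm if allocation is equal (my assumption). No symptom outcome enters this calculation.

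**2. Model.** Let p be the true sedation rate in an arm, q1 the non-response if sedated and q0 the non-response if not sedated. Then:
- rate seen among repliers = p(1−q1) / [p(1−q1) + (1−p)(1−q0)]
- non-response in the arm = p·q1 + (1−p)·q0

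The documents give none of p, q0 or q1. I assume p = 20% on placebo and 40% on gabapentin, with three non-response pairs that average 19.5%, 19% and 22%, close to the plan's 20%.

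| q0 / q1 | Placebo seen | Gabapentin seen | Difference (true 20 points) | Silent, placebo / gabapentin |
|---|---|---|---|---|
| 15% / 30% | 0.14/0.82 = 17.1% | 0.28/0.79 = 35.4% | 18.4 | 18% / 21% |
| 10% / 40% | 0.12/0.84 = 14.3% | 0.24/0.78 = 30.8% | 16.5 | 16% / 22% |
| 10% / 50% | 0.10/0.82 = 12.2% | 0.20/0.74 = 27.0% | 14.8 | 18% / 26% |

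With 60 per arm and a two-sided 5% normal test, power to see the excess is 54%, 50% and 44%. It is 58%, 58% and 56% if the same losses are random, and 67% with no loss. Much of the drop is therefore ordinary loss of data; the informative part adds 4, 8 and 12 points.

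**3. Odds ratio.** The odds seen in an arm are [p/(1−p)] × [(1−q1)/(1−q0)]. If q0 and q1 are the same in both arms, the second factor cancels. True odds ratio: (0.40/0.60)/(0.20/0.80) = 2.67. First row of the table: (0.28/0.51)/(0.14/0.68) = 2.67. It is the same in every row.

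**4. Other true rates.** Hold pooled non-response at 20%, with sedated women silent three times as often.
- True 40% vs 60% (q0 = 10%, q1 = 30%): the difference seen is 19.7 points.
- True 60% vs 80% (q0 = 8.3%, q1 = 25%): 55.1% vs 76.6% is seen, a difference of 21.5 points, larger than the true 20.

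**5. Silence that also depends on arm.** True 20% vs 40%, with q0 = 15% in both arms.
- Sedated women silent 40% on gabapentin and 20% on placebo: 0.24/0.75 = 32.0% vs 0.16/0.84 = 19.0%, difference 13.0.
- The reverse: 0.32/0.83 = 38.6% vs 0.12/0.80 = 15.0%, difference 23.6.

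**6. What a sensitivity analysis can bound.** Counting every missing reply as sedated gives p + (1−p)·q0: 32% vs 49%, 28% vs 46% and 28% vs 46% in the three rows. Each is above the true rate in its arm, so it is a valid upper bound there. The differences are 17, 18 and 18 points, and neither these nor the differences among repliers reach the true 20. The contrast needs arm-specific extremes. In the last row, placebo lies between 10% and 28% and gabapentin between 20% and 46%, so the difference lies between 20 − 28 = −8 and 46 − 10 = +36 points. That range is wide, but it contains 20.

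**The case against.** A reader might infer that the planned test will understate gabapentin's excess sedation, and so hide the drug's main harm. The documents do not support that.
- They give no reply rates by sedation status or by arm. Pain, ordinary sleep, codeine (prescribed in both arms) or a wish for privacy could also cause silence.
- Even if drowsiness does reduce replies, the odds ratio may be untouched and the risk difference can move either way. High rates are not far-fetched for a question about being more tired than usual, asked in the hours after a clinic procedure.
- Somnolence is named together with dizziness, not alone, and Section 12 cites gynecologic studies with no significant increase in either.

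The plan also has features that limit the loss. Payment depends on answering all five texts at each contact, participants are told when the texts will come, and no cut-off for late replies is stated. There are three in-person assessments.

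These points narrow the concern without removing it. Payment cannot make a sleeping woman answer. The baseline check precedes the drug, the five-minute check is early, and the admission check has no stated look-back. Section 3 itself says that hysterectomy studies are not good proxies for this setting. An unknown direction is also a reason to show the missing replies.

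It is fair to add that comparing non-response between arms will settle little by itself. For 18% vs 26% with 60 per arm, power is about 18% and the 95% interval is about ±15 points.

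**Conclusion.** The gap is real and concerns a secondary safety outcome. Between discharge and admission, the two side effects that the plan names as most common are known only for women who reply. Up to 20% may not reply, and Section 8 does not say how that is handled.

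If drowsy women reply less often, each arm's sedation rate is understated. Under the assumed rates the shortfall is about 3 to 8 points on placebo (20% seen as 12-17%) and 5 to 13 points on gabapentin (40% seen as 27-35%). If silence is unrelated to sedation there is no bias. The risk difference shrinks at low to moderate rates. It may move either way at high rates or if silence also depends on arm. The odds ratio is unbiased if silence depends only on sedation. All rates used here are assumptions, so the sizes are illustrative. The missing provision can be checked directly in the text.

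**What to change.** 1. **Section 7, step 10.** Ask every woman in both arms, in the same blinded wording, whether she was unusually drowsy or dizzy at any time since leaving clinic. For each unanswered round, ask why it was missed. Report these recalled answers separately from the real-time replies.
2. **Section 8, reporting.** Give the proportion not answering each symptom question by arm and time point, with a 95% confidence interval for the difference. State the denominator of every symptom rate. Treat the comparison as descriptive.
3. **Section 8, sensitivity analysis.** Count missing replies as symptomatic to give an upper bound for each arm's rate. For the between-arm difference, give arm-specific best-case and worst-case bounds, because the first device does not bound the difference.

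Item 1 costs two short questions in an existing interview. Items 2 and 3 need no new data, only a few table rows and two or three sentences. Section 5 aims to finish enrolment in January 2018 and this version is dated 2018, so item 1 may reach only the remaining women; items 2 and 3 can be done regardless.

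Downsides: next-day recall is less reliable than a real-time reply, ordinary sleep may be reported as drowsiness, and the best/worst-case bounds will be wide. None of the three replaces the main figure among repliers.

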Participants will be assigned a unique study number for use on source documents and participant study charts. These documents will be kept in a locked file cabinet accessible only to study staff. Data from participant's study charts and text message contact will be entered into a secure database. No identifying information will be entered into the study database. Only password-protected, institutionally secured UC Davis computers will be used for data entry and analysis. Data will be reviewed by the principal investigator and research coordinator to ensure accuracy and completeness. The research database will be banked indefinitely for the purpose of future research questions and will contain only de-identified information as above.

A cell phone will be purchased for the purposes of this study. This phone line will be dedicated to the study and will be password protected. It will stay with the principal investigator or research assistant during the times when participant follow-up is occurring. Outside of this time, the secured cell phone will be kept in a locked file cabinet with restricted access. Since the phone will not be attended at all times, participants will be given the standard UC Davis contact information for all clinical and study-related questions at any time. Our division has a dedicated phone line for family planning research patients that is covered by research personnel during the day (who have close access to an assigned family planning physician) and forwarded to the on call family

PROTOCOL TITLE: Gabapentin for pain control after osmotic dilator insertion and prior to D&E procedure: a randomized controlled trial

planning attending or fellow at night. All family planning attendings and fellows will be trained as study personnel. The cell phone's remote data erase function and location service will both be activated to protect study data in the event that the phone is lost or stolen.

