Prior to first contact, the research assistant will program the participant into the phone contact list with their study number and preferred phone number. The Android SMS Scheduler application will record all scheduled and sent text messages. The application's template function will be used to ensure all outgoing text messages are uniform. Incoming text messages are returned to the cell phone's default text message application. The study cell phone will only be connected to the password protected, secure institutional wireless internet connection. The study cell phone's mobile data will be turned off at all times to improve security. Text message responses will be input into the study database on a weekly basis and the participant's contact information and text messages deleted from the phone.

9) Data Banking

The entire research study database, which will contain only de-identified data, will be banked indefinitely for the purposes of future research analysis.

10) Provisions to Monitor the Data to Ensure the Safety of Subjects

- Safety data will be collected throughout the study – participants will be asked about potential medication side effects.
- Adverse event (AE): adverse experience such as symptom, physical exam finding, or worsening of a preexisting condition that has a temporal association with research participation. Causal relationship with study treatment is not necessary to designate an AE.
- Given the contact of participants via text message in this study, significant breach in participant privacy will also be classified as an adverse experience. At enrollment, participants will be counseled to ensure they are making a fully informed decision to participate knowing that there will be text message contact with them. They will be counseled regarding ways to withdrawal if safety becomes a concern. If this occurs, study staff will list safety-related withdrawal as an AE and review as below.
- Serious adverse event (SAE): adverse event that requires hospitalization, causes significant disability, is life threatening or results in death.
- AEs will be logged and reviewed by an investigator for study drug relationship
- Any SAE will be reported to the principal investigator once identified. The participant will be managed medically as indicated. All source data will be

PROTOCOL TITLE: Gabapentin for pain control after osmotic dilator insertion and prior to D&E procedure: a randomized controlled trial

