As noted in Section 7, participant privacy is a consideration as participants will be contacted while outside the healthcare setting and other individuals may have access to their cell phone. To protect participants' privacy, only the above text content will be sent, which is generic in nature and does not identify pregnancy or abortion. Participants will be given a form listing the times when the text messages will be sent to them so they can keep the phone with them. Participants will be advised to also password protect their own phone and change settings so text message content is not displayed on their phone without unlocking it. Participants will also be given the 24-hour contact information for family planning research coordinators/physicians that can remove them from the study and discontinue any future text message contact if they wish.

The study cell phone will only be used in the small research office/preoperative clinic area and will be in a locked cabinet when not in the hands of research staff. As noted, it will not be connected to the mobile data network and will only be used over the secure, password protected UC Davis wireless internet. Data will be erased from the phone on a weekly basis after import into the secure database. The phone's remote erase and location functions will be enabled for another layer of security. Family planning physicians at the University of Hawaii who are completing a similar study (randomized controlled trial of Pregabalin versus placebo for pain with medication abortion, communicating with participants at home via text message through the SMS Scheduler Android App) have provided insight into use of the text messaging app/privacy protection and have reported no privacy-related adverse events.

The form given to participants that includes text message times will identify the UC Davis Department of Obstetrics and Gynecology, as well as Family Planning physicians, in the contact information for participant questions or concerns. This does not pose additional risk to our participants as **all** patients in our pre-operative abortion clinic are given a folder containing copies of their signed abortion

PROTOCOL TITLE: Gabapentin for pain control after osmotic dilator insertion and prior to D&E procedure: a randomized controlled trial

consents, post-dilator and pre/post abortion care instructions, along with abortion support references.

13) Potential Benefits to Subjects

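### The plan states no route by which remote erase and location would reach the study phone once it leaves institutional wireless coverage

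*Combined protocol and SAP*

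**What the plan says.** Section 8 (Data Management) describes one dedicated study phone. Of that phone it says that the "remote data erase function and location service will both be activated to protect study data in the event that the phone is lost or stolen". Section 12 (Privacy risk) relies on the same functions: "The phone's remote erase and location functions will be enabled for another layer of security".

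Both sections also restrict the phone's connections. Section 8 states "The study cell phone's mobile data will be turned off at all times to improve security" and "The study cell phone will only be connected to the password protected, secure institutional wireless internet connection". Section 12 repeats both limits: "it will not be connected to the mobile data network and will only be used over the secure, password protected UC Davis wireless internet".

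On location and custody, Section 12 says "The study cell phone will only be used in the small research office/preoperative clinic area", with a locked cabinet at other times. Section 8 says of the phone, "It will stay with the principal investigator or research assistant during the times when participant follow-up is occurring". Section 7 sets the length of that follow-up: "Participants will be contacted via text message at 2, 4, and 8 hours after dilator insertion".

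Section 8 also says that the phone has a password, that each woman is entered in its contact list by study number and phone number, and that replies are transferred and cleared once a week.

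**The concern.** A stolen phone will usually leave the building, and a lost one may. That is when remote erase and location are most needed, and it is also when the phone has neither of the internet connections at issue: mobile data is off and institutional wireless is out of range. The safeguard and the restriction are each stated twice, and no section reconciles them.

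What is at stake is confidentiality. Section 12 names privacy as one of the two main categories of risk to participants, and Section 10 classes a significant privacy breach as an adverse experience. A reader of the protocol is told that a layer of protection exists for loss or theft. As specified, it is not shown to work in the off-site case.

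**Working it through.** The protocol has no figure to reproduce here. The check sets the statements side by side and then sizes the exposure.

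**Can a command reach the phone?**

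- *Phone lost or taken but still connected to institutional wireless.* An internet path exists, so erase and location could work. This includes the only area in which Section 12 says the phone is used.
- *Phone outside institutional wireless, commands sent over the internet.* Mobile data is off and no other network is permitted, so there is no path. A command would not arrive while the phone stays offline.
- *Phone outside institutional wireless, commands sent by cellular text.* Texting works with mobile data off, since the study depends on it. This route is not excluded, but the protocol does not mention it.

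The gap is therefore the second case, and it rests on the assumption of internet delivery.

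**Could the phone be off site?** Section 12 confines use to the office and clinic area. Section 8 has it stay with a member of staff during follow-up, which runs to 8 hours after insertion. The documents give no insertion times. As an assumption, an insertion at 10:00 puts the last text at 10:00 + 8 h = 18:00, and a later insertion puts it later. The plan does not say that staff stay on site until then.

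**What would be exposed?**

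- Planned accrual (Section 5): 121 women in 12 months, so 121 / 52 = 2.33 women per week.
- Busy week, assuming Poisson counts with mean 2.33: P(X ≤ 4) = 0.91 and P(X ≤ 5) = 0.97, so the 95th percentile is 5.
- Replies per woman: 5 questions × 3 text rounds = 15 at most.
- Content: phone number, study number, pain scores, pill counts, and answers on dizziness and tiredness.

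With weekly clearing, the phone holds up to about a week of this material.

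**What still protects it off site?** The password needs no connection. Deletions already made limit how many women are on the phone. The generic wording limits what a finder could learn. Locked storage and staff custody make loss less likely but do not act after it. The documents do not mention device encryption, a local erase or a text-triggered erase. That silence does not show that they are absent.

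**The case against.** A reader might infer that remote erase and location can never reach the phone, so that the protocol claims a safeguard the design does not have. The documents do not support that. The functions are to be activated for a phone that is lost or stolen, and one misplaced or taken on site and still connected can be reached. The protocol never says how commands travel, so internet-only delivery is an assumption, and a text-triggered erase remains possible. Silence on the route is a missing detail, not proof of failure.

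A reader might also infer that only the password would be left, or that a lost study phone would reveal an abortion. Neither follows. Weekly deletion and generic wording also limit exposure, and Section 12 says that the messages sent do not identify pregnancy or abortion. The statement in Section 7 that compromised privacy could put a woman at risk concerns people with access to the participant's own phone, not loss of the study phone.

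Finally, mobile data is off by deliberate choice, for security. Turning it back on would trade one risk against another, and the documents do not show that data could be limited to the erase service alone. That objection stands, and the fix below leaves mobile data off.

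What the objection does not answer is the off-site case: no section says how erase or location would work there.

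**Conclusion.** The point holds in limited form. As specified, and assuming that commands travel over the internet, remote erase and location would work only while the phone is still connected to institutional wireless. They have no stated route once it is off site.

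The size is modest: the records of about 2.3 women in a typical week and about 5 in a busy one (Poisson assumption), readable only after custody has failed and the password has been defeated. Randomisation, the primary outcome, sample size and analysis are not affected. This is a minor participant-privacy correction. It is worth making because privacy is a named primary risk and the remedy is cheap.

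**What to change.** Leave mobile data off and make three changes.

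1. Before first use, test remote erase and location with the phone off the institutional network. If the test fails, remove from Sections 8 and 12 the statement that these functions protect a lost or stolen phone, or limit it to loss within institutional wireless coverage.
2. Enable and state a safeguard that needs no connection: device encryption, with automatic local erase after a set number of failed unlock attempts. This helps whichever route the remote commands use.
3. In Sections 8 and 12, replace weekly entry and deletion with entry and deletion on the next working day after each participant's last text contact. This shortens the time that each woman's details stay on the phone. It also limits how many replies an accidental local erase could destroy.

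The cost is one test, a phone setting, a short amendment and slightly more frequent data entry. A small risk remains of losing replies not yet entered, including those at 8 hours, the time point of the study hypothesis (Section 2). The third change keeps that risk low.
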